Currently, the G6PD status of a patient is most often defined by the patient's G6PD phenotype, characterized by analysis of total activity in blood lysate [6,7]. This method, considered the gold standard, is a costly and complex quantitative laboratory based spectrophotometric test. While quantitative laboratory test can clearly identify subjects with all ranges of G6PD activities (including those with intermediate levels who may also be at risk of severe hemolysis), these methods require an equipped laboratory and skilled personnel.

In field settings, the most commonly performed tests use qualitative devices such as the fluorescent spot test (FST) or the CareStart test, which can only discriminate gross deficiencies from all the other phenotypes [8-10]. These qualitative tests are adequate for males who are either deficient or normal in G6PD status. Because females carry two alleles of the G6PD gene, they can present as deficient, intermediate, or normal for G6PD activity. Qualitative tests cannot discriminate intermediate from normal G6PD activity. Quantitative tests are required for better case management for women, especially in anticipation of the availability of tafenoquine which is indicated for use only for women and men with normal G6PD activity.

Given the target populations where antimalarial drugs are required, often in remote rural settings, point-of-care (POC) G6PD tests are required to support broader availability of primaquine and, in the future, tafenoquine. For treatment of women whose enzymatic activity is estimated to be normal by qualitative testing but is still too low for treatment of high-dose primaquine or tafenoquine, a quantitative portable device will be needed to obtain more accurate levels of G6PD activity to ensure appropriate and safe treatment.

To date, no routine screening of G6PD deficiency is performed in Brazil before primaquine use for radical cure of *P. vivax* malaria. However, recent data suggest that G6PD screening could be cost-effective and that implementation of this additional step in malaria diagnosis and treatment is being considered by the Ministry of Health.

In order to enable the use of radical cure treatment for *P. vivax* malaria, PATH is working to accelerate the development of G6PD tests that meet the following criteria:

- Quantitative
- Measures G6PD activity normalized by hemoglobin (IU/g Hb)
- Measures hemoglobin (g/dL)
- Corrects for enzyme temperature dependence
- Finger stick (<10 ul)

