3.1 Statistical analyses

Data will be entered into a Microsoft Excel database with built-in validation rules to minimize data entry errors. Descriptive statistical analysis, including calculating point estimates, distribution, and frequencies of responses, will be used to summarize and characterize the study population.

3.1.1 Diagnostic accuracy and performance:

For the purposes of this study, an individual will be considered G6PD deficient (case) if they test positive by the spectrophotometric gold standard. The primary success criterion will be focused on the ability to identify G6PD deficient participants correctly, such that both the POC G6PD test and the spectrophotometric gold standard test should both accurately identify all G6PD deficient specimens (with < 20% normal) as deficient.

The performance of the POC G6PD against the spectrophotometric gold standard will be determined by calculating the sensitivity and specificity. Sensitivity and specificity of the SD Biosensor (SDB) G6PD assay were calculated as per Domingo et al. [14]. In summary, an adjusted male median will be calculated for both the POC G6PD and spectrophotometric gold standard test from where the 30%, 40%, 70% and 80% cutoff levels for the two tests will be used to categorically define G6PD deficient cases.

Sensitivity calculations will be determined by the following method: TTP=true and test positive (positive by reference assays according to case definition and positive by the POC G6PD test), FNTP=false negative true positive (positive by reference assays according to case definition and negative by the POC G6PD test). Sensitivity = $TTP/(TTP+FNTP)$.

Specificity will be determined by the following method: TPTN=test positive true negative (negative by reference assays according to case definition and positive by POC G6PD test), TTN=Test and true negative (negative by reference assays according to case definition and negative by POC G6PD test). Specificity= $TTN/(TTN+TPTN)$.

Sensitivity and specificity results will be reported using 95% confidence intervals.

3.1.2 Accuracy between G6PD activity and Hemoglobin methods:

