3.2 Sample size

The sample size for this study is based on the expected prevalence of G6PD deficiency at the study site and by data requirements set by WHO PQ [15]. This requires obtaining samples from participants with a range of G6PD activity levels. The WHO PQ process defines these levels as such:

Table 2. G6PD activity thresholds

Females	
Deficient	G6PD activity < 30% of the adjusted male median
Intermediate	G6PD activity 30%-80% of the adjusted male median
Normal	G6PD activity > 80% of the adjusted male median
Males	

Deficient	G6PD activity < 30% of the adjusted male median
Normal	G6PD activity > 30% of the adjusted male median

According to the Target Product Profile (TPP), the novel POC G6PD will need to be at least 95% sensitive for detecting G6PD activity levels at 30% to 80% of normal enzyme activity. Assuming a sensitivity of 95%, with a confidence interval of 95%, and a 1% to 2% maximum marginal error, a minimum of 162 participants with deficient and intermediate G6PD activity will be needed. To account for any possible device/diagnostic failures or compromised blood samples due to insufficient blood, signs of blood degradation, or contamination, to the sample size will need to increase by 20%. In addition, to ensure there are sufficient deficient and intermediate participants in the case of a lower-than-expected enrollment rate of these two groups occurs, at least 200 participants of each group should be included in the study. This additional enriched sample will also serve to meet the requirements of the WHO PQ. Eligible adults and children aged 2 years old and above will be recruited for potential participation though diagnostic performance analysis will not be segmented based on age.

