5.4 Test result return and follow up

Results of point of care malaria microscopy will be returned to participants as per standard care. Results of the POC hemoglobin testing will be returned to participants

immediately after testing, as the test is registered for use in Brazil. Study staff will relay results and counsel participants who test positive for malaria or anemia according to the results return script (Appendix C3). Any participants identified as malaria positive or anemic will be counselled and referred for follow-up. Participants in the clinic will receive standard care at the clinic and participants recruited through household surveys will be referred for follow-up to the local health agent as per routine practice.

In Brazil, no routine screening to identify individuals with G6PD deficiency is implemented in the public health system and treatment with primaquine is recommended for all people infected with *P. vivax* with the exception of pregnant women and children under six months of age. However, information regarding the G6PD status of a vivax patient is critical for informing safe and effective treatment recommendations. As per WHO guidelines for the treatment of malaria, standard treatment of primaquine should not be given to patients who are G6PD deficient in order to avoid primaquine-induced hemolysis and patients who are G6PD intermediate should be monitored closely for signs of hemolysis [18].

Initial evaluations by PATH indicate that the POC G6PD test is able to identify G6PD deficiency (see section 7.1). As such, participants who test positive for *P. vivax* malaria and are found to be G6PD deficient or intermediate will be notified of their POC test result in order to make that information available to their health provider when determining their course of treatment for vivax malaria.

Participants found to be vivax positive and G6PD deficient

For vivax positive participants found to be G6PD deficient with the POC test (G6PD test result of below 30% of normal enzymatic activity), the study team will provide referral with the recommendation that primaquine treatment be withheld until confirmatory testing can be completed. Confirmatory testing will take no more than one week to complete. At that time, through referral to the health agent, *P. vivax* patients who are identified as G6PD deficient can receive treatment for the blood stage disease (treatment with chloroquine) immediately.

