If the results of the reference assay confirm the results of the POC G6PD test (enzymatic activity less than 30%) they will be contacted and informed of the result and their G6PD status by validated reference assay. If the results of the reference assay indicate that the participant is G6PD normal, they will be contacted, informed of the result, and referred to a health agent to receive with standard treatment for liver stage disease, as per national guidelines.

Participants found to be vivax positive and G6PD intermediate

For vivax positive participants found to be G6PD intermediate with the POC test (G6PD test result between 30 and 80% of normal enzymatic activity), the study team will provide referral with the recommendation that primaquine treatment be closely monitored for signs of hemolysis given the increased risk of hemolysis associated with moderate G6PD deficiency.

If the results of the reference assay confirm the results of the POC G6PD test (enzymatic activity between 30-80%) they will be contacted and informed of the result and their G6PD status by validated reference assay. If the results of the reference assay indicate that the participant is G6PD normal, they will be contacted and informed of the result and referred to a health agent to receive with standard treatment for liver stage disease, as per national guidelines.

Among any vivax positive participants, those known to be G6PD intermediate or deficient based on previous studies may receive a false negative result on the POC investigational test in this study and found to be G6PD normal. In the event that this occurs, the study team will proceed in the same manner as for participants found to be vivax positive and POC G6PD deficient or intermediate. See Figure 3.

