If any participants are confirmed *P. vivax* malaria positive and G6PD deficient at the point of care, the study team will relay this the information as part of the counselling. The study team will refer the participant to a health for treatment, equipped with counselling information that the participant may be G6PD deficient or intermediate and if given primaquine treatment is at an increased risk of severe hemolysis. This will enable the participant to receive immediate treatment for the blood stage infection and provide better information to the health worker responsible for case management, including any treatment for the liver stage infection. The participant's G6PD status will then be confirmed by a reference assay to inform further case management as necessary. The table below outlines the study procedure and subsequent follow up action.

Table 5. Case management

Study test	Result		Action
Hemoglobin	Normal hemoglobin levels (by national guidelines)		No action
	Mild moderate or severe anemia (by national guidelines)		Counselling re: the results of the hemoglobin test and referral to the health system for follow-up case management. This may involve the provision of iron tablets or other treatment depending on severity.
G6PD deficiency	Negative test result on investigational device (G6PD normal)		No immediate action. If reference assay is discrepant and identifies G6PD intermediate or deficient status, the study team will conduct follow-up counselling (Appendix C2).
	Positive test result on investigational device (G6PD deficient or intermediate)		Result to be confirmed at the laboratory with the reference assay. If confirmed G6PD deficient or intermediate with the reference assay, the study team will conduct follow-up counselling (Appendix C2).
Malaria	Negative test result (no malaria)		G6PD and hemoglobin managed as above, otherwise no action
	Positive test result (confirmed malaria)	POC G6PD normal	Patient referred to health system for free treatment: 3 days CQ and 7 days PQ. If confirmed deficient or intermediate with reference assay, provide follow up counselling as described above.
		POC G6PD intermediate	Patient referred to health system for free treatment: 3 days CQ and 7 days PQ. Provide counseling re: G6PD intermediate status and recommend additional monitoring and attention to possible signs/symptoms of hemolysis. If confirmed deficient or intermediate with reference assay, provide follow up counselling as described above.

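### Case cutoffs at 40%, 70% and 80% carry no sex rule although Table 2 calls men above 30% normal, and accuracy is planned at own-median POC cutoffs that may not be those used at testing

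*Combined protocol and SAP*

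**What the plan says.** Section 3.1.1 calculates an adjusted male median for the POC test and another for the reference assay, and states that the "30%, 40%, 70% and 80% cutoff levels for the two tests will be used to categorically define G6PD deficient cases". It presents this as a summary of a cited set of recommendations. It gives no sex restriction, does not name the sample from which the POC median is taken, and states no POC cutoff in U/g Hb.

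Two places treat men as having two classes only. Table 2 in section 3.2, introduced as the WHO prequalification levels, lists an intermediate class under females but not under males, for whom normal is "G6PD activity > 30% of the adjusted male median". Section 1.0 says: "These qualitative tests are adequate for males who are either deficient or normal in G6PD status".

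Three places use the middle range without mentioning sex. The target product profile (TPP) sentence in section 3.2 requires the POC test to be "at least 95% sensitive for detecting G6PD activity levels at 30% to 80% of normal enzyme activity". Section 5.4 defines a POC intermediate as a "G6PD test result between 30 and 80% of normal enzymatic activity". Table 5 in section 5.6 groups POC intermediate with POC deficient as a positive result.

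On timing, section 5.4 says that participants with vivax malaria who are POC deficient or intermediate "will be notified of their POC test result in order to make that information available to their health provider". A deficient result there is a "G6PD test result of below 30% of normal enzymatic activity". Reference confirmation comes later. Section 2.0 makes the classification of results by trained health workers part of the primary objective.

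**The concern.** There are two separate matters.

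(a) Sex. Two analysts working from this plan could build different 2x2 tables at 40%, 70% and 80%. One would count a man at 75% of the male median as a case at 80%; the other, following Table 2, would count him as normal. The 80% result could then partly describe men whom the plan elsewhere defines as normal, and those men would sit close to the cutoff, where two assays disagree most easily.

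(b) Cutoffs. Sensitivity and specificity are planned at percentages of the POC test's own male median. If that median comes from the completed study data, it was not available when results were classified at testing. The estimates may then describe recentred cutoffs and not the classes that users delivered. This reaches every cutoff, including 30%.

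**Working it through.** **The plan's own figures.** The only numeric percent-of-median cutoffs are the reference thresholds in Table 7 (section 7.1), with a 100% value of 9.3 U/g Hb. They reproduce: 0.30 × 9.3 = 2.79 (stated 2.8), 0.70 × 9.3 = 6.51 (6.5), 0.80 × 9.3 = 7.44 (7.4).

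**(a) Men affected.** The documents give no sex split and no between-person CV, so both are assumed. The précis plans 1,700 normal and 200 intermediate participants; half of 1,900 is 950 non-deficient men. Assume male activity is normal around the male median with CV 10–25%. The number between 30% and fraction f of the median is 950 × [Φ((f − 1)/CV) − Φ((0.3 − 1)/CV)].

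| CV | 30–40% | 30–70% | 30–80% |
|---|---|---|---|
| 10% | 0 | 1 | 22 |
| 15% | 0 | 22 | 87 |
| 20% | 1 | 63 | 151 |
| 25% | 5 | 107 | 199 |

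For example, at CV 15% and f = 0.80: 950 × Φ(−1.333) = 950 × 0.0912 = 87. The plan expects about 200 intermediates in all.

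**(a) Effect on accuracy.** This was simulated in 24 scenarios of 200 replicates, each with 2,000 participants. Assumptions: 75 deficient and 925 normal men; 25 deficient, 200 intermediate and 775 normal women; median 9.3; reference/POC measurement errors of 3/6%, 5/8% or 8/12%.

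- Sensitivity at 80%: pooled is about 0.5 to 3.7 points below women only.
- Sensitivity at 70%: women minus pooled is about −1.7 to +0.8 points, so either sign.
- Specificity at 80%: differs by at most 0.6 points.
- Men above 30% as a share of all cases at 80%: from 21/334 = 6% to 189/632 = 30%.

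The top of that range sits badly with the planned yield. Taking 189 men and 100 deficient from 632 leaves 343 non-deficient women below 80%, against 200 planned. At the low end 334 − 21 − 100 = 213, close to plan.

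**(b) What own-median scaling does.** Let the POC test read k × x for true activity x, with true male median M. Its own median is k × M, so a result is below the cutoff when k × x < f × k × M, that is when x < f × M. The factor k cancels, and proportional calibration error disappears from sensitivity and specificity. An additive offset c does not cancel: the condition becomes x < f × M − (1 − f) × c.

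For illustration only, take k = 1.15, M = 9.3 and f = 0.30. The own-median cutoff is 0.30 × 1.15 × 9.3 = 3.21 on the POC scale, which corresponds to x = 2.79. Had a cutoff of 2.79 been fixed beforehand, results below it would correspond to x < 2.79/1.15 = 2.43. A person between 2.43 and 2.79 would be above that fixed cutoff but scored as detected in the own-median analysis. The documents do not say that 2.79 is used in the field.

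**(b) Would the Bland-Altman limits catch it?** Section 3.1.2 accepts ±2.0 U/g Hb. A 15% bias shifts results by 0.15 × 9.3 = 1.395 at the median, so passing needs a difference SD of at most (2.0 − 1.395)/1.96 = 0.31. In simulation with a POC test 15% high or low, 0 of 1,800 replicates passed; at CV 15% and errors 5/8%, 15% high gave limits of −0.68 to +3.23. A 5% high bias with errors 3/6% gave −0.80 to +1.66, which passes. Large bias is thus likely to be seen, but the limits do not count misclassified people.

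**The case against.** On sex, section 3.1.1 summarises a cited method that may hold its own sex rule and cannot be seen here. Table 2 stands in the sample size section and is not declared the case definition for analysis. The 70% and 80% cutoffs can be read as activity thresholds for everyone, in line with the TPP sentence, section 5.4 and Table 5. On that reading the all-participant result is valid and only its label is loose. This stands as far as it goes: the plan has to say which reading it intends. It does not support the opposite step, that 70% and 80% cases must be restricted to females. The sections conflict, and that choice depends on reconciling them.

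On the cutoffs, a reader might infer that those analysed cannot be those used at testing. The documents do not go that far. Section 3.1.1 says a median will be calculated without expressly naming the data, and a value fixed in advance would remove the timing problem. Field cutoffs may also be held in the instructions for use, the training material or appendices not reproduced here. What stands is narrower: the natural reading is a median from study data, and no field cutoff is visible in the text.

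A reader might also divide Table 7's POC thresholds (4.2, 6.0, 6.2 U/g Hb) by 30%, 70% and 80% and conclude that no single POC median fits. That shows nothing here. They are ROC-optimal thresholds, which need not be percentages of a median, and they are not said to be the field cutoffs.

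Finally, user classification has its own endpoint with an 85% criterion (sections 3.0 and 3.1.3). It is assessed by questionnaire on simulated tests, so it does not measure whether participants' samples were classified correctly.

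**Conclusion.** Both parts hold in limited form.

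(a) As written, men whom Table 2 calls normal count as cases at 40%, 70% and 80%. The 30% analysis and the primary success criterion are untouched by this. The size is modest: about 22–199 men at 30–80%, 1–107 at 30–70% and 0–5 at 30–40%, with roughly 0.5–3.7 points of sensitivity at 80%. A few points could matter against a 95% target. All of these figures rest on an assumed sex split, CV, activity distribution and measurement error; the upper end goes with more intermediate women than the plan expects.

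(b) The planned sensitivity and specificity may not describe the classification delivered at testing, which is part of the primary objective, and own-median scaling hides proportional calibration error from them. The size cannot be computed without the field cutoff, and a loss of accuracy is not shown.

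**What to change.** 1. In section 3.1.1, report sensitivity and specificity at 40%, 70% and 80% separately for females and males. Keep 30% in both sexes. Label any all-participant result at the higher cutoffs an activity-threshold analysis.
2. Reconcile sections 3.1.1, 3.2 (Table 2 and the TPP sentence), 5.4 and 5.6 (Table 5) on whether the intermediate class applies to men, then state which result is the headline. No clinical rule is proposed here.
3. Before data are seen, state in section 3.1.1 the numeric U/g Hb POC cutoffs used to classify results at testing, wherever they are now held. Report sensitivity and specificity at those cutoffs alongside the own-median analysis, and name the sample used for the POC median.

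The cost is wording and extra 2x2 tables on data already collected. If the headline at 80% were female-only, precision would fall slightly. The 95% half-width at 95% sensitivity is 1.96 × √(0.95 × 0.05/n): 2.5 points for n = 300 and 2.8 points for n = 225, where 225 assumes 200 intermediate and 25 deficient women.

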Endpoints	
 • Sensitivity and specificity of G6PD tests compared to the Pointe Scientific G6PD Analyzer 
 ◦ accuracy between POC G6PD test measure of G6PD activity and a reference assay ◦ accuracy between POC G6PD test measure of hemoglobin and a reference assay • Comparison of POC G6PD test results using capillary and venous samples • Percent of trained health workers who can accurately comprehend key messaging included in the test packaging and labels • Percent of trained health workers who can accurately interpret the result output and classify results as either normal, invalid, deficient or intermediate
Population	
Based on estimated G6PD prevalence, we expect to recruit approximately:
 
 • 1,700 people with normal G6PD activity levels • 200 people with intermediate G6PD activity levels • 100 people with deficient G6PD activity levels 
For the usability portion, we will recruit 15 trained health workers.

Study sites	This study will be conducted in Manaus and Porto Velho.
Study Duration	9 months (estimated)

Table of Contents

1.0	Background and rationale for the study	4
2.0	Study objectives	6
3.0	Study design	6
4.0	Research participants	10
5.0	Study procedures	11
6.0	Consent process	21
7.0	Study products	22
8.0	Benefit and risk considerations	25
9.0	Study and safety monitoring	26
10.0	Ethical considerations	27
11.0	Confidentiality and data management	28
12.0	Study limitations	30
13.0	Investigator responsibilities	30
	References:	31

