Quantitative agreement for both G6PD activity and Hb values between the POC G6PD test and spectrophotometric gold standard will be graphically analyzed. Correlation graphs between the POC G6PD test and gold standard test will be plotted and an R-squared value will be determined. An R-squared value of greater than 0.9 for both G6PD activity and Hb will be considered acceptable.

Bland Altman plots, where differences between the G6PD POC tests and gold standard test are plotted against the gold standard value, together with the 95% limits of agreement. Acceptable limits of agreements for Hb should be within +/-1.0 g/dL (based on a 6% estimate for allowable method bias) and for G6PD activity should be within +/-2.0 U G6PD/g Hb (based on a 15% estimate for allowable method bias). All statistical analyses will be performed using Stata 13.0.

The data comparison for the analyses is outlined below:

Table 1. Comparison methods

Index test by sample type	Reference method	
	G6PD normalized for Hb	Hb
Venous	Point Scientific G6PD from venous specimen normalized for Hb from venous specimen	Hb from venous specimen
Capillary		Hemocue Hb from finger stick

3.1.3 Diagnostic usability:

Response choices to usability assessment questionnaires will include both multiple-choice and open-ended responses. The usability questionnaire will include a brief assessment of health literacy using a validated health literacy instrument. Participants will be encouraged to comment on any aspects of the label or results they find confusing or inadequate. Success criteria are defined as 85% correct participant response to questions that assess key messages and results interpretation. Any participant that obtains 85% or above correct responses to the usability questionnaire will be considered to accurately comprehend the product IFU and labelling. Analyses will include descriptive statistics and a tabular presentation of findings.

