7.0 Study products

7.1 SDB G6PD Analyzer

The STANDARD G6PD Analyzer is designed to measure the quantitative determination of total-hemoglobin concentration and G6PD enzymatic activity in fresh human whole blood specimen based on reflectometry assays. The test is intended to aid in the identification of people with G6PD deficiency. The test is currently registered in Brazil but not used by the public health system or considered part of routine use in malaria case management. PATH has conducted some initial laboratory evaluations which suggest that the test aligns to performance specifications outlined in the target product profile [19]. The test has CE mark and is registered for use in other malaria endemic countries.

Performance STANDARD G6PD test when stress tested under multiple temperature and humidity conditions. The STANDARD G6PD values were compared to the Pointe Scientific generated G6PD values for all 314 data points generated across the following ambient conditions: 22 °C, 32 °C 50% humidity, 37 °C 50% humidity, and 37 °C 75% humidity. ROC analysis was performed to generate the optimal thresholds for the STANDARD G6PD test. CI refers to the confidence interval, NA, not applicable.

Table 7. Performance of SD Biosensor STANDARD G6PD test

Threshold (Pointe Scientific value U/gHb)	Optimal STANDARD G6PD (U/gHb)	Sensitivity (95% CI)	Specificity (95% CI)
30% (2.8)	4.2	100 (95.1 – 100.0)	96 (93.0 – 98.3)
70% (6.5)	6.0	98 (92.4 – 99.7)	99 (96.8 – 99.9)
80% (7.4)	6.2	86 (80.7 – 93.9)	99 (95.9 – 99.7)
100% (9.3)	NA	NA	NA

Figure 4. SD Biosensor STANDARD G6PD Test

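### R-squared above 0.9 is a pass mark for quantitative agreement, but it does not measure agreement, shifts with the spread of the sample, and can disagree with the plan's own limits of agreement

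*Combined protocol and SAP*

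**What the plan says.** Section 3.1.2 opens with "Quantitative agreement for both G6PD activity and Hb values between the POC G6PD test and spectrophotometric gold standard will be graphically analyzed". It then sets two numerical standards.

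- Correlation: "An R-squared value of greater than 0.9 for both G6PD activity and Hb will be considered acceptable".
- Bland-Altman limits: the interval "for G6PD activity should be within +/-2.0 U G6PD/g Hb (based on a 15% estimate for allowable method bias"). The Hb counterpart is +/-1.0 g/dL, which the plan ties to a figure of 6%.

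The section does not say whether both standards must be met, which one governs if they differ, or in what sample mix R-squared is to be judged. It gives no derivation of 0.9.

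The synopsis expects "1,700 people with normal G6PD activity levels", "200 people with intermediate G6PD activity levels" and "100 people with deficient G6PD activity levels". Section 3.2 repeats about 100 deficient for Brazil, but also asks for at least 200 in each of the deficient and intermediate groups. Section 4.1 says that about half of the participants come from an enriched sample with known G6PD status. Section 3.1.1 places the primary success criterion elsewhere, on correct identification of deficient participants.

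**The concern.** Agreement asks how far apart two readings on the same person are. R-squared asks how well a straight line, any straight line, relates them, and it scales the scatter by the spread of the sample. Two consequences follow.

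- Adding a constant to every point-of-care reading, or multiplying every reading by a constant, leaves R-squared unchanged.
- With the measurement error held fixed, R-squared rises as the reference values spread out. For G6PD, enrolling more deficient or intermediate people does this. For Hb, a wider range of age, sex and anemia does it.

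The G6PD spread here is partly a recruitment choice. At stake is the verdict on two listed accuracy endpoints (G6PD activity and Hb), in a study meant to support WHO prequalification and product registration. A test could meet the stated limits and still be declared unacceptable on R-squared. If R-squared alone were enough, the reverse could happen.

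**Working it through.** **Plan's own figures.** The 0.9 has no derivation, so there is nothing to reproduce. The expected deficient count does reproduce: 2,000 x 0.05 = 100.

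**Inputs.** From the documents: the planned mix of 1,700/200/100; the limits +/-2.0 U/g Hb and +/-1.0 g/dL; the 30% and 80% class boundaries (section 3.2, Table 2); and 100% activity = 9.3 U/g Hb on the reference assay (section 7.1, Table 7). Assumed:
- normals have mean 9.3 and SD 1.2 to 2.5;
- intermediates are uniform over 30-80% of 9.3 (mean 5.115, variance 4.65^2/12 = 1.802);
- deficients are uniform over 0-30% of 9.3 (mean 1.395, variance 2.79^2/12 = 0.649);
- the error is constant and unrelated to the reference value.

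**Formula.** For an unbiased test, R-squared = V/(V + s^2), where V is the variance of the reference values and s is the SD of the differences. Exactly at the G6PD limit, s = 2.0/1.96 = 1.02 and s^2 = 1.041.

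**One case in full (SD among normals 2.0).**
- 100 deficient: within-group variance = 0.85 x 4.00 + 0.10 x 1.802 + 0.05 x 0.649 = 3.613. The overall mean is 8.486 and the between-group variance 4.214. V = 7.826, and R-squared = 7.826/8.867 = 0.883.
- 200 deficient (1,600/200/200): V = 3.445 + 6.539 = 9.984, and R-squared = 9.984/11.025 = 0.906.

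**Range for a G6PD test exactly at +/-2.0.** The last column is the limit half-width to which R-squared = 0.9 corresponds in the planned mix: 1.96 x sqrt(V/9).

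| SD among normals | V, planned mix | R-squared, 100 deficient | R-squared, 200 deficient | Equivalent half-width |
|---|---|---|---|---|
| 1.2 | 5.65 | 0.844 | 0.884 | 1.55 |
| 1.5 | 6.34 | 0.859 | 0.892 | 1.64 |
| 2.0 | 7.83 | 0.883 | 0.906 | 1.83 |
| 2.5 | 9.74 | 0.903 | 0.919 | 2.04 |

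To reach 0.9 at the limit, the reference SD must be at least 3 x 1.02 = 3.06. The planned mix gives 2.38 to 3.12.

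**Hb exactly at +/-1.0 g/dL.** s = 1.0/1.96 = 0.510 and s^2 = 0.260. R-squared is 1.44/1.700 = 0.847 at Hb SD 1.2, 2.25/2.510 = 0.896 at 1.5, and 3.24/3.500 = 0.926 at 1.8. The break-even SD is 3 x 0.510 = 1.53. The documents give no Hb SD.

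**The opposite direction (planned mix, SD among normals 1.5, V = 6.339).**
- A test reading 3.0 too high with error SD 0.5: R-squared = 6.339/6.589 = 0.96, limits 3.0 +/- 0.98 = +2.0 to +4.0.
- A test reading 0.7 x reference with error SD 0.4: R-squared = 3.106/3.266 = 0.95. The mean difference is -0.3 x 8.486 = -2.55 and the SD of differences sqrt(0.09 x 6.339 + 0.16) = 0.855, so the limits are -4.2 to -0.9.

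Both pass on R-squared and fail on the limits.

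**Both standards met.** An unbiased test with error SD 0.7 in the same mix has R-squared = 6.339/6.829 = 0.928 and limits of +/-1.37.

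**The case against.** The strongest reply is that bias is already covered. The Bland-Altman limits stand in the next paragraph of section 3.1.2, and both biased tests above fail them. If both standards bind, R-squared is only an additional, often stricter, hurdle. A proportional scale error would not harm classification either, because section 3.1.1 takes percentage cutoffs from a separate adjusted male median for each test. All of this stands. It narrows the harm to failing a test that meets the limits, unless R-squared alone suffices. The plan does not say which reading applies.

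It is also fair that the size rests on SDs the documents do not give: at an SD among normals of 2.5, a test at the limit passes.

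A reader might infer more than the documents support:

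- That the two standards contradict each other. They do not; a precise, unbiased test meets both. They can give different verdicts, with no rule to settle them.
- That case mix rather than test quality decides the result. Precision matters as well: in the planned mix at SD 1.5, R-squared falls from 0.928 to 0.859 as the error SD goes from 0.7 to 1.02.
- That deficient enrolment affects both analytes. It matters for G6PD; for Hb it is the Hb range.
- That results from the three countries would not be comparable. Section 3.2 plans the same 5% deficient and 10% intermediate in Brazil and India. Only Ethiopia differs, and the stated intention is to combine the data.
- That Table 7 in section 7.1 shows a scale difference (POC 4.2, 6.0 and 6.2 against reference 2.8, 6.5 and 7.4). The text there says "ROC analysis was performed to generate the optimal thresholds for the STANDARD G6PD test", from temperature and humidity stress testing. Such cutoffs are not a calibration line.

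**Conclusion.** The point holds, within limits. R-squared above 0.9 does not suit the purpose section 3.1.2 gives it, and it can return a different answer from the limits of agreement beside it. For G6PD in the planned mix it usually acts as a tighter limit, about +/-1.55 to +/-2.04 against the stated +/-2.0, for an assumed SD among normals of 1.2 to 2.5. At SD 2.0, a test exactly at the limit moves from fail to pass between the plan's two deficient counts. For Hb the verdict at the limit turns on whether the Hb SD exceeds about 1.53 g/dL. If both standards bind, the cost is rejecting a test that meets the limits; if R-squared alone sufficed, a biased test could pass. These results assume constant error and the mixture described. The primary success criterion is untouched, so this is a secondary-analysis correction, but one worth making before the data are analysed.

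**What to change.** In section 3.1.2, report R-squared as a description only, and state that the Bland-Altman limits already given (+/-2.0 U/g Hb and +/-1.0 g/dL) are the acceptance criterion for quantitative agreement.

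Add, as supporting analysis without a pass mark:
- Passing-Bablok regression, or Deming regression with a stated error-variance ratio, giving slope and intercept with 95% CIs;
- the POC-minus-reference difference with 95% CI at the reference values for 30%, 70% and 80% activity.

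The limits should stay as the acceptance rule because the documents provide no margins for slope, intercept or difference at a cutoff. If Deming regression is chosen, the ratio has to be stated: section 5.2.5 plans duplicates of the reference tests, but the POC test has only one capillary reading and one venous replicate, so its error variance is not directly available from like-for-like duplicates.

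The cost is a change of wording and one extra regression on data already being collected. The downside is that a familiar summary figure no longer counts as a pass.
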